# 2 PROTOCOL AMENDMENT/REVISION HISTORY

DNDi

RD 777/34920

DNDi- 0690- 02

Protocol Version/ Date	Type of Amendment	Amendment Rationale	Sections Affected	Summary of Amendment / Changes to the Protocol
V1.0/23 September 2020	N/A	N/A	N/A	N/A
V2.0/13 October 2020	N/A	Amendment requested in MHRA notice of grounds for non- acceptance letter dated 12 October 2020.	Section 3 (Synopsis) and Section 10.2.2 (Stopping Criteria)	The following wording: "If events are confirmed significantly more frequent in the active group, dose escalation will only proceed once an appropriate substantial amendment has been submitted and received regulatory and ethical approval from the relevant ethics committee and competent authority." have been changed to: "if any of the stopping criteria occurred in a subject receiving DNDI-0690 the trial will put on halt and further dosing can be resumed only once an appropriate substantial amendment has been submitted and received regulatory and ethical approval from the relevant ethics committee and competent authority."
V3.0/07 December 2020	Non-substantial	To document administrative changes and to correct discrepancies throughout the protocol.	Signature page, Synopsis, Section 10.7.1 (Flow Chart), Section 10.7.7.1 (PK blood sampling for DNDI-060 and metabolite), Section 10.7.10 (plasma samples for iohexol) and throughout protocol.	
 
Change of DNDi responsible physician (Medical Responsible)
 
Increased acceptable deviation window for vital signs and 12-lead ECG
 
Correction of Troponin baseline in Table 8 Part C (Day 1 pre-dose, not Day -1).
 
Post-Study vital sign added in the Table 8 Part C flowchart.
 
Day 4 urine PK sample removed from Table 7 Part B flowchart and synopsis.
 
Weight measurement removed from Day -2 in Table 8 Part C flowchart.
 
Part B dosing will only be OD dosing.
 
Footnote of Table 10: Clarification on source documentation location for subject eligibility.
 
Table 6 & 7, Footnote 5 has been updated.
 
Table 8 Footnote 10: Text clarified about Iohexol assessment at Post-study Follow-up visit.
 
Table 9 updated to reflect change in blood volume as tube sizes have changed.
 
Sample processing information updated.
 

DNDi RD 777/34920 DNDi- 0690- 02

# Clinical Study Protocol

Final V3.0/ Date 07 December 2020

Page 6 of 109

Confidential

		• Plasma samples for DNDI-0690 and metabolite: tube size modified (4 mL instead of 6 mL).
		• Blood sample for the determination of plasma iohexol levels: tube size modified (4 mL instead of 5 mL).
		• Added triglycerides in biochemistry panel.
		• Discrepancies and typos were corrected throughout the protocol.

Confidential

Final V3.0/ Date 07 December 2020

Page 7 of 109

### 3 SYNOPSIS

DNDi- 0690- 02

RD 777/34920

**DNDi** 

NAME OF COMPANY: Drugs for Neglected Diseases initiative (DNDi)

NAME OF INVESTIGATIONAL MEDICINAL PRODUCT: DNDI- 0690

NAME OF ACTIVE INGREDIENT: nitroimidazooxazine

**TITLE OF STUDY**: A Phase I, Double-blind, Randomised, Single Centre, Parallel-group, Multiple-dose, Dose-escalation, Placebo-controlled Study of the Safety, Tolerability and Pharmacokinetics of DNDI-0690 after Oral Dosing in Healthy Subjects

PRINCIPAL INVESTIGATOR: [name]

STUDY CENTRE: Simbec-Orion Clinical Pharmacology

[name], UK

#### **CLINICAL PHASE: I**

#### **OBJECTIVES:**

#### Part A & B

#### **Primary Objective**

• To assess the safety and tolerability of DNDI-0690 after multiple oral doses in healthy subjects in fasted conditions.

### **Secondary Objective**

• To investigate plasma and urinary pharmacokinetics (PK) of DNDI-0690 after multiple oral doses in healthy subjects in fasted conditions.

### **Exploratory Objectives**

- To investigate any potential changes to renal toxicity markers in urine.
- To assess the effect of DNDI-0690 on Holter electrocardiogram (ECG) parameters.
- To compare PK bioanalysis in fixed volume dry blood spots versus PK bioanalysis in plasma samples.
- To investigate the metabolite profile of DNDI-0690 after multiple dosing.
- To assess variation of mRNA expression in full blood before and after exposure to the drug (Transcriptional Profiling).

### Part C

## **Primary Objective**

• To evaluate renal function (glomerular filtration rate (GFR)) before and after administration of DNDI-0690 in healthy subjects in fasted condition at maximum well tolerated dose tested in Part A or below.

### **METHODOLOGY:**

The study will be conducted in three parts (Part A, Part B and Part C).

**Part A** of the study is a single centre, double-blind, randomised, placebo-controlled, parallel-group, multiple oral dose, dose-escalation study to assess the safety, tolerability and PK of DNDI-0690 after multiple oral doses in the fasted condition in healthy male and woman of non-childbearing potential (WONCBP) subjects.

**Part B** of the study is a single centre, double-blind, randomised, placebo-controlled, multiple oral dose study to assess the pharmacodynamic effect of DNDI-0690 on cardiac function after multiple oral doses at the supratherapeutic dose in the fasted condition in healthy male and WONCBP subjects.

DNDi RD 777/34920 DNDi- 0690- 02

Final V3.0/ Date 07 December 2020

Confidential

Page 8 of 109

**Part C** of the study is a single centre, double-blind, randomised, placebo-controlled, multiple oral dose study to evaluate the renal function (measured Glomerular Filtration Rate (mGFR)) before and after multiple oral doses in the fasted condition in healthy male and WONCBP subjects.

### Part A: Multiple Ascending Dose Cohorts (Cohorts 1-4)

Part A will consist of up to 4 cohorts of 9 subjects. Subjects will be randomly assigned to receive an oral dose of active IMP (6 subjects) or matching placebo (3 subjects) for 10 days in a sequential escalating manner with a minimum of 7 days interval between two cohorts.

In Part A, each cohort will follow a sentinel dose-escalation schedule; two (2) subjects will be dosed on the first dosing day of each cohort (1 subject on active IMP and 1 subject on matching placebo). The remainder of the cohort (5 subjects on active IMP and 2 subjects on matching placebo) will be dosed a minimum of 48 hours later pending confirmation of an acceptable safety profile in the dose-leader cohort by the Principal Investigator (PI), or medically-qualified designees who are familiar with the study protocol and Investigator's Brochure (IB).

The planned starting dose for Cohort 1 is 400 mg of DNDI-0690 once a day for 10 days. Doses to be administered in Cohorts 2 to 4 will be determined based on emerging PK and safety data. The number of daily doses may be increased to 2 by implementation of a twice a day (BID) dosing regimen if the number of capsules in a single intake is raising concerns of acceptability. This decision will be made by the Safety Review Committee (SRC) prior to each cohort and will apply to all subjects within a cohort.

Dose escalation between cohorts in Part A (and between Part A and Part B) will be temporarily stopped pending evaluation of all available data if any of the following criteria are fulfilled:

• A serious adverse reaction (*i.e.* a serious adverse event (SAE) considered at least possibly related to the IMP administration) occurs in one subject.

Or

• Severe non-serious adverse reactions (*i.e.* severe non-serious AE considered as, at least possibly related to the IMP administration) occur in two subjects in the same cohort, independent of within or not within the same system organ class.

Or

- If two or more subjects in the preceding dose group experience any of the following:
  - Alanine aminotransferase (ALT) or aspartate aminotransferase (AST) >3x upper limit of normal (ULN), considered clinically significant and IMP related.
  - Serum Cystatin C (Cys C) increase > 25%, confirmed after repeat assessment 24-48h apart, and considered IMP related.
  - o Ratio of microalbuminuria/creatininuria >300 mg/g and considered IMP related.
  - An increase in corrected QT interval by Fridericia's formula (QTcF) value of >60 msec from baseline (average of baseline triplicate values) or an absolute QTcF >500 msec, both confirmed by repeat measurement after 20 minutes in resting position, and considered IMP related.

Or

- If one or more subjects in the preceding dose group experience:
  - o An increase in troponin I concentration which is considered clinically significant by the Investigator (with reference to the change from baseline value) and considered IMP related.

Or

• If the dose in a single subject is anticipated to exceed an AUC from time of dosing to the end of the dosing interval (AUC0-tau) of  $\geq$ 100 µg\*h/mL. These limits are based on the exposure observed at the 20 mg/kg in cynomolgus monkeys (no observed adverse effect level (NOAEL): AUC0-24 of 101 µg\*h/mL in male and 111 µg\*h/mL in females).

DNDi RD 777/34920 DNDi- 0690- 02

Final V3.0/ Date 07 December 2020

Confidential

Page 9 of 109

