#### IMP ADMINISTRATION

**DNDi** 

RD 777/34920

DNDi- 0690- 02

Capsules of DNDI-0690 100mg and 200 mg have been chosen as the formulation for this study. The number of capsules to be administered will vary depending on the dose selected by the SRC upon review of data (safety and PK) from the previous cohort.

Table 1 Description of DNDI-0690 doses

Part A	Dose		Incurace from the provious dass
rart A	mg	mg/kg/day*	Increase from the previous dose
Cohort 1	400 OD	5.7	
Cohort 2	To be decided	To be decided	2 to 3 times and/or change from OD to BID
Cohort 3	To be decided	To be decided	2 to 3 times and/or change from OD to BID
Cohort 4	To be decided	To be decided	2 to 3 times and/or change from OD to BID
Part B	maximum of 3600	maximum of 51.5	
Part C	To be decided	To be decided	Highest dose tested in Part A and well tolerated, or below

\* assuming a 70-kg person

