## 8.5 Toxicology

### 8.5.1 Regulatory Toxicology Studies

The non-clinical safety of DNDI-0690 was assessed in repeated dose toxicity studies in rats and monkeys following oral administration of the compound daily for up to 4 weeks.

In rats, a first GLP 14-day toxicity study was conducted with DNDI-0690 formulated in polyethylene glycol (PEG) 400 and administered as single daily doses up to 250 mg/kg/day. In

DNDi RD 777/34920 DNDi- 0690- 02

Final V3.0/ Date 07 December 2020

Confidential

Page 39 of 109

this study, the NOAEL was set at 100 mg/kg/day (AUC24 on Day 14 of 93.6 and 149  $\mu g \cdot h/mL$  in males and females, respectively) since some histopathological changes in the liver (hepatocellular hypertrophy) and adrenals (cortical vacuolation and hypertrophy) were detected at the dose of 250 mg/kg/day.

Subsequent toxicity studies both in rats and in monkeys were performed using DNDI-0690 formulated as nanosuspension.

In the GLP 4-week repeated dose toxicity study in rats, only minimal reduction of body weight and food consumption, with concomitant slight decrease in globulin and total cholesterol, were seen at doses of 200 and 1000 mg/kg/day (100 and 500 mg/kg BID 6-h apart). No other effects were evidenced. Based on these findings, the dose of 40 mg/kg/day was the NOEL and the dose of 1000 mg/kg/day was the NOAEL.

In the GLP 4-week toxicity study in monkeys, doses of 20, 100 and 400 mg/kg/day (10, 50, 200mg/kg BID 6-h apart) were selected. One female died at the dose of 100 mg/kg/day and another at 400 mg/kg/day on Days 23 and 29, respectively. Deaths were related to severe effects on the heart and the kidneys, the animals were severely dehydrated, and the adverse effects on the heart being likely a consequence of renal toxicity. In other monkeys treated at these dose levels, noteworthy effects of DNDI-0690 included renal effects in females and histological changes in the testes in males (see below). Changes in the kidneys were characterized by tubular dilatation, cell degeneration and/or basophilia, associated with increases in creatinine and urea. Kidney changes completely recovered, as evidenced at the end of a 7-week recovery period. In this study, no effects were observed at the dose of 20 mg/kg/day that was considered as the NOAEL in monkeys after 4-week administration.

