A Pathology Working Group (PWG) was constituted to review the data on testes. For the 7–day study, the PWG concluded that the testicular effect of vacuolation was a background change and that the effects seen were all considered as fixation artefact and thus the testicular histology was all concluded to be within the normal. In the case of the 28-day study, the PWG confirmed following review the presence of changes in the testes of animals at the two highest doses of 100 and 400 mg/kg/day (the same animals as in the initial report) where the finding was described by the PWG as segmental tubular dilation with associated thinning/atrophy of the seminiferous epithelium. This distribution could suggest a potential relationship to treatment. However, based upon the segmental nature of the finding, the frequent unilateral distribution and the fact that this finding has been described in a number of publications as a background change in young cynomolgus monkeys, it was concluded that the findings in the testes were a background lesion and unrelated to treatment. In conclusion, treatment with DNDI-0690 for 7 or 28 days is not considered to induce any testicular changes or toxicity.

Confidential

Final V3.0/ Date 07 December 2020

Page 40 of 109

Table 3 Summary of Toxicokinetic and Pharmacokinetic Parameters for DNDI-0690\*

Species / Day	Gender	Type of study	Dose PO (mg/kg/day)	C max (µg/mL)	AUC 0-24 (μg.h/mL)
Rat /	M	Toxicology TK	1000 (500 bid) NOAEL 28 days	$11.3 \pm 0.693$	180 ± 22.5
Day 28	F	Toxicology TK	1000 (500 bid) NOAEL 28 days	16.9 ± 1.47	307 ± 36.8
Monkey /	M Toxicology TK		20 (10 bid) NOAEL 28 days	$8.03 \pm 0.367$	101 ± 7.85
Day 28	F	Toxicology TK	20 (10 bid) NOAEL 28 days	$9.03 \pm 6.78$	111 ± 61.2

\* methodology, additional doses and time-points available in the IB

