### 8.7 Risk/Benefit Assessment

No benefit will be observed in healthy volunteers.

The risk/benefit ratio of the proposed study is considered acceptable. Several measures to minimize the risks to healthy subjects have been taken with respect to the following study design elements:

- For each cohort in Part A and Part B, 2 subjects (1 subject on active drug and a subject on matching placebo) will be dosed and monitored for 48 hours prior to dosing the rest of the cohort.
- Dose escalation (during Part A and between Part A and Part B) will be done in a stepwise, controlled manner, with dose escalation only being permitted after full evaluation of the available safety data from the previous cohort by the SRC.
- Clinical laboratory monitoring: At time of study entry, study participants are required to have safety laboratory values within acceptable ranges. Serial measurements of safety laboratory parameters (Biochemistry and haematology which include platelet count, renal/liver function tests, renal integrity monitoring) and coagulation parameters are planned with interim reviews as defined in the SRC charter.
- Close cardiac safety monitoring by regular ECG assessments.
- Study eligibility: The healthy subject/patient inclusion and exclusion criteria have been incorporated to minimize any risk of an exaggerated pharmacological effect of DNDI-0690.
- The evaluation of GFR by a reference method in Part C will be performed at the end of the trial. The dose level used in Part C will be tested in Part A and will have no impact on the safety of the volunteers.
- The starting dose in Part A of this study is 400 mg once daily for 10 days which is considered to be safe and is well below the highest dose level of 3600 mg DNDI-0690 administered in the SAD study. It is expected that the maximum values of  $C_{max}$  and  $AUC_{0-24}$  in individual subjects in Part A Cohort 1 will be well below the PK stopping criteria of  $C_{max} \ge 8000$  ng/mL or  $AUC_{0-24} \ge 100,000$  ng,h/mL.

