#### 10.2.2.3 Dose Escalation Stopping Criteria

Dose escalation between cohorts in Part A (and between Part A and Part B) will be temporarily stopped pending evaluation of all available data if any of the following criteria are fulfilled:

• A serious adverse reaction (*i.e.* a SAE considered at least possibly related to the IMP administration) occurs in one subject.

Or

• Severe non-serious adverse reactions (*i.e.*, severe non-serious AE considered as, at least possibly related to the IMP administration) occur in two subjects in the same cohort, independent of within or not within the same system organ class.

Or

• If two or more subjects in the preceding dose group experience any of the following:

DNDi RD 777/34920 DNDi- 0690- 02

Final V3.0/ Date 07 December 2020

Confidential

Page 50 of 109

- o ALT or AST >3xULN, considered clinically significant and IMP related.
- Serum Cys C increase > 25%, confirmed after repeat assessment 24-48h apart, and considered IMP related.
- o Ratio of microalbuminuria/creatininuria >300 mg/g and considered IMP related.
- o an increase in QTcF value of >60 msec from baseline (average of baseline triplicate values) or an absolute QTcF >500 msec, both confirmed by repeat measurement after 20 minutes in resting position, and considered IMP related.

Or

- If one or more subjects in the preceding dose group experience:
  - o an increase in troponin I concentration which is considered clinically significant by the Investigator (with reference to the change from baseline value) and considered IMP related.

Or

• If the dose in a single subject is anticipated to exceed an AUC0-tau of  $\geq 100 \, \mu g^*h/mL$ . These limits are based on the exposure observed at the 20 mg/kg in cynomolgus monkeys (NOAEL: AUC0-24 of 101  $\mu g^*h/mL$  in male and 111  $\mu g^*h/mL$  in females).

Or

• If the dose in a single subject is anticipated to exceed a  $C_{max}$  of  $\geq 8.0 \ \mu g/mL$ . These limits are based on the exposure observed at the 20 mg/kg in cynomolgus monkeys (NOAEL:  $C_{max}$  of  $8.03 \ \mu g/mL$  in males and  $9.03 \ \mu g/mL$  in females).

Dose escalation between cohorts in Part A will be limited to a maximal 3-fold increase, and 2-fold increase between Part A and Part B, depending on safety and tolerability data and predicted exposure (both AUC and  $C_{max}$ ).

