  - Ae%: % of dose excreted in urine over each collection interval (0 to 24 h post-dose).
  - CLR: Renal clearance

If BID dosing, AUC0-10, AUC0-10/D, AUC0-10h,norm will be added on Day 1 and Day10.

Derived PK parameters will be listed along with the points used to calculate  $k_{el}$  (lower, upper and number used) and  $R^2$  adjusted. The derived PK parameters will also be summarised. The descriptive statistics presented will be N, n, arithmetic mean, geometric mean (with the exception of  $T_{max}$ ), SD, coefficient of variation (CV%), minimum, median and maximum.

**Dose Proportionality/Independence (Part A and Part B):** For Day 1 and Day 10 (Part A) OR Day 1 and Day 5 (Part B), dose proportionality will be assessed by performing a regression analysis of the log-transformed  $C_{max}$ ,  $AUC_{0-\tau}$  and  $AUC_{0-inf}$  (Day 10 for Part A and Day 5 for Part B only) values versus the log-transformed dose using the power model with a fixed effect for log(dose). For each parameter a point estimate and 95 % confidence interval (CI) will be calculated for the slope of the regression line.

For Day 10 for Part A and Day 5 for Part B, dose independence will be assessed for t½ and CL/F by performing a regression analysis of the untransformed parameters versus dose with a fixed effect for dose. For each parameter a point estimate and corresponding 95 % CI will be calculated for the slope of the regression line.

**Steady-State** (**Part A and Part B**): For each dose level, log-transformed trough concentration levels at pre-dose each day (Day 2 to Day 10 for Part A and Day 2 to Day 5 for Part B) will be subjected to a mixed effects analysis of variance (ANOVA) with study day as a fixed effect and subject as a random effect in order to establish whether and when steady-state has been attained for each dose level. Back-transformed ratios for the comparisons of each consecutive day (*i.e.* Day 3/Day 2) will be presented along with corresponding 90 % CI.

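### Under BID dosing the Part A cap on AUC0-tau permits about 200 µg·h/mL per day, roughly twice the monkey NOAEL AUC0-24 on which it is based

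*Protocol*

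**What the plan says.** The Synopsis (Part A) and 10.2.2.3 list the criteria that stop escalation. One reads "If the dose in a single subject is anticipated to exceed an AUC from time of dosing to the end of the dosing interval" of 100 µg·h/mL or more. The abbreviation list also defines AUC0-tau by the dosing interval, not by 24 hours. Both places give the source of the limit: "These limits are based on the exposure observed at the 20 mg/kg in cynomolgus monkeys", with NOAEL AUC0-24 values of 101 µg·h/mL (males) and 111 µg·h/mL (females). Table 3 in 8.5.1 shows that this dose was divided: "20 (10 bid) NOAEL 28 days".

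The Synopsis keeps twice-daily dosing open in Part A: "The number of daily doses may be increased to 2 by implementation of a twice a day (BID) dosing regimen", if capsule number becomes a concern. Table 1 lists the step for each of Cohorts 2 to 4 as "2 to 3 times and/or change from OD to BID". The evening dose follows the morning dose by 10 hours (10.5.3.1), and Day 10 has a morning dose only. For BID, 10.9.2.5.4 says that AUC0-10 parameters "will be added on Day 1 and Day10".

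Elsewhere the limit appears as AUC0-24. Section 8.6.1, reporting the single-dose study, gives it as 100,000 ng·h/mL over 24 hours. Section 8.7 expects that exposures "in individual subjects in Part A Cohort 1 will be well below the PK stopping criteria of" the same AUC0-24 value.

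**The concern.** A cap taken from a 24-hour exposure should be applied to a 24-hour exposure. Under OD dosing, AUC0-tau and AUC0-24 are the same quantity. Under BID, AUC0-tau covers one of two intervals, while the monkey figure behind the limit already covers two doses. The human cap per day is then about double its stated basis.

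The kidney is the main target organ (8.5.1), and the limit exists to hold individual subjects at or below the NOAEL exposure. At the next monkey dose level there were renal effects, and "One female died at the dose of 100 mg/kg/day and another at 400 mg/kg/day". A committee applying 10.2.2.3 literally could approve 10 days of a BID regimen at which some subjects pass the NOAEL AUC0-24 without the exposure criterion being met.

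**Working it through.** **Plan's own figures.** Section 8.6.1 puts the highest single-dose exposures 60.5% (Cmax) and 57.4% (AUC0-24) below the cap. 1 − 3160/8000 = 60.5% and 1 − 42,600/100,000 = 57.4%. Table 4's accumulation ratio at 3600 mg is 44,900/32,800 = 1.37. All reproduce.

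**Daily exposure the cap allows.** Two intervals, each just under 100, give about 200 µg·h/mL per day. 200/101 = 1.98 and 200/111 = 1.80.

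**Predicted exposure at 2400 mg/day as 1200 mg BID.** Inputs are from Table 4 (men), using the linear superposition of 10.3.1.
- Twice the 1200 mg steady-state AUC0-tau: 2 × 23,600 = 47,200 ng·h/mL. Twice its AUC0-inf: 2 × 25,100 = 50,200.
- Against 3600 mg OD, like for like: 47,200/44,900 = 1.05 and 50,200/47,100 = 1.07.
- 2400 mg OD, interpolated: slope = ln(44,900/23,600)/ln 3 = 0.585, and 23,600 × 2^0.585 = 35,400. Because exposure is sub-proportional to dose, splitting 2400 mg raises the predicted daily AUC by a factor of 47,200/35,400 = 1.33.

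**Individual subjects.** Assume a log-normal spread with sigma = √ln(1 + CV²). The CVs are 64.2% (Table 4, 1200 mg), 23.5% (Table 4, 3600 mg) and 40% as an assumed middle value.
- One subject over 100 per day: P = 1 − Φ(ln(100/47.2)/sigma).
- One subject over 100 in a half-day interval: P = 1 − Φ(ln(100/23.6)/sigma).
- Any of 6 active subjects: 1 − (1 − P)^6.

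| CV | sigma | Over 100 per day: one subject | any of 6 | Over 100 per interval: one subject | any of 6 |
|---|---|---|---|---|---|
| 23.5% | 0.232 | 0.06% | 0.4% | about 0 | about 0 |
| 40% | 0.385 | 2.6% | 14% | 0.009% | 0.05% |
| 64.2% | 0.587 | 10.1% | 47% | 0.7% | 4% |

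At CV 64.2%, the per-interval rule identifies about 0.7/10.1 = 7% of the subjects who pass 100 per day. With 50.2 in place of 47.2, the any-of-6 daily figures are 0.9%, 20% and 54%.

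**What the escalation review would see.** Section 10.2.1 calls for Cmax and AUC0-24 from the 24 hours after the last dose. At 1200 mg, AUC0-12 is 13,400, AUC0-24 is 19,700 and AUC0-inf is 25,100. Assume a mono-exponential tail after 12 h: k = −ln(1 − 6,300/11,700)/12 = 0.0644 per hour. Then AUC0-14 is 14,815, and the part after 14 h is 25,100 − 14,815 ≈ 10,290. The Day 10 AUC0-24 in a BID cohort is the sum of:
- the Day 10 morning dose, 19,700;
- earlier morning doses, 25,100 − 19,700 = 5,400;
- earlier evening doses, 10,290.

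The total is 35,390, or 70% of 50,200.

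**Cmax cap.** Predicted steady-state Cmax at 1200 mg OD is 1,990 ng/mL against a cap of 8,000, so this criterion does not stand in for the AUC one.

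**The case against.** BID is permitted only if the number of capsules is a concern. The single-dose study gave 18 capsules at once, and 2400 mg needs 2400/200 = 12. This makes BID less likely, but the protocol plans for it in three of four cohorts.

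The predicted mean at 1200 mg BID is about half the limit, and on the model above only about 0.7% of men would pass 200 per day even at the largest CV. This stands: 200 is what the wording allows, not what is expected.

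The exceedance probability depends heavily on the CV. At 3600 mg, where exposure is closest to 1200 mg BID, the CV is 23.5% and the risk nearly vanishes. The highest individual AUC0-24 at that dose was 42.6 µg·h/mL, though after a single dose. This also stands, so 47% should not be quoted without the range.

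The committee could use a daily AUC anyway: the limit cites an AUC0-24, 10.2.1 asks for AUC0-24, the rule concerns anticipated exposure, and AUC0-10 and troughs are collected. That is sensible practice, but the criterion is not written that way and the AUC0-24 listed for review omits the evening dose.

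Several stronger readings are not supported. The cap does not cease to limit daily exposure; it limits it to about 200. Section 8.7 is not a rival rule for BID cohorts: it describes Cohort 1, which is OD, and is correct there. A predicted excess of 5 to 7% over 3600 mg OD does not show that Part A would surpass Part B's maximum. The protocol gives no exposures at 100 or 400 mg/kg/day in monkeys, so how near 100 to 200 µg·h/mL lies to toxicity cannot be judged from it.

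**Conclusion.** The point holds for BID cohorts only. The operative rule sets a per-interval quantity against a limit taken from a two-dose daily exposure, and so admits about 1.8 to 2 times the NOAEL AUC0-24. This is an error in the rule as written, not a detail left for later. Neither the Cmax cap nor the planned AUC0-24 review closes the gap.

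Its practical size is uncertain. At 1200 mg BID the mean is comfortably inside the limit, and the chance that at least one of 6 active subjects passes 100 per day runs from 0.4% to 47% across the CVs considered (on the 47.2 mean). These figures assume linear superposition, log-normal spread and Table 4's data in men. Section 8.6.1 reports higher exposure in women, so for a mixed cohort they are, if anything, low. It should be corrected before any BID cohort is dosed.

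**What to change.** - Synopsis and 10.2.2.3: state the cap as predicted steady-state AUC0-24 of 100 µg·h/mL or more, summed over both doses when BID is used.
- 10.2.1: for BID cohorts, require a daily AUC that includes the evening dose, obtained by superposition from the planned Day 1 and Day 10 profiles. This is the method 10.3.1 already uses.
- Synopsis, Table 1 and 10.2.2.3: state that the 3-fold limit applies to total daily dose. Read per dose, Table 1 could allow a step from 400 mg OD to 1200 mg BID, which is 2400/400 = 6-fold per day.

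The 2400 mg maximum in 10.3.1 is already stated per day and needs no change. The cost is protocol wording, with no additional subjects or samples.
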